6.3.2.2 FIH Maximum Dose Consideration

No adverse toxicological findings were observed in 2-week repeat dose GLP-compliant toxicology study in rats at doses up to 60 mg/kg; however, body weight loss and associated clinical observations were considered adverse in dogs at 50 mg/kg. The NOAEL was determined to be the mid-dose of 15 mg/kg/day in dogs, which produced an AUC (705,000 h*ng/mL) that was less than half the rat NOAEL AUC (2,470,000 h*ng/mL); the dog was considered to be the most sensitive species. As per the International Council for Harmonisation of Technical Requirements for Pharmaceuticals for Human Use (ICH) “Guidance on Nonclinical Safety Studies for the Conduct of Human Clinical Trials and Marketing Authorization for Pharmaceuticals M3(R2)” [13], for situations where only one species demonstrates adverse toxicities, the maximum clinical dose will be limited to AUC exposure at the NOAEL in the species showing toxicity or half the AUC at the NOAEL in the species without toxicity. Thus, the AUC of TAK-510 in the clinic will not exceed 705,000 h*ng/mL, which is the dog NOAEL AUC.

Preliminary data from other studies recently analyzed have helped refine [REDACTED]

[REDACTED] The doses that are predicted to maintain concentration in the efficacious range and allow for optimal onset of response within 30 minutes are planned to be evaluated.

Given the available formulation [REDACTED] and feasibility limitation of maximum administered volume of 1 mL per SC injection, [REDACTED] is the highest planned dose predicted to be evaluated in Part 1. The predicted exposure [REDACTED] will be [REDACTED] below the dog NOAEL (most sensitive species; $AUC_{\infty} = 705,000$ h*ng/mL).

6.3.2.3 FIH Proposed Dose Regimen for the SRD Cohorts

The proposed dose regimen with target PK and safety margins for select proposed doses is presented in Table 6.b.

Table 6.b Human Dose-Related Concentrations and Exposures for Select Proposed Doses in Part 1

Dose ^a (µg)	C _{max} (ng/mL)	AUC _∞ (h*ng/mL)	Safety Margin NOAEL Exposure
5			

AUC: area under the plasma concentration-time curve; AUC_∞: area under the plasma concentration-time curve from time 0 to infinity; C_{max}: maximum observed plasma concentration; NOAEL: no-observed-adverse-effect level; PK: pharmacokinetic.

Exposure at NOAEL in dog 705,000 h*ng/mL (AUC).

Values represent geometric mean.

^a Single dose administered.

^b Preliminary observed PK parameters.

^c Predicted assuming linear PK from observed [REDACTED] preliminary human PK data from this ongoing study.

It is planned that up to 17 doses may be explored with a maximum escalation factor between cohorts [REDACTED] at lower exposures and [REDACTED] at high exposures.

Dose levels may be adjusted based on emerging safety and available PK data from previous cohorts, and after discussion between the sponsor and investigator. Doses may be repeated if safety and tolerability are acceptable, or lower doses may be studied to increase data within the dose range. Any decision to resume dosing at the current dose level or to escalate the dose will be made jointly by the investigator and the sponsor after careful evaluation of all available blinded data.

6.3.2.4 Rationale for Dosing Interval

Multiple dose cohorts (Part 2) will be administered TAK-510 once daily. [REDACTED]

The dosing regimens selected for Parts 2 and 3 will have a projected AUC_∞ that will not exceed an AUC_∞ of 705,000 h*ng/mL or the highest AUC_∞ determined to be tolerated in Part 1.

6.3.2.5 Rationale for Dose Titration and Redosing After Washout

Part 3 of the study is intended to evaluate whether dose titration can result in a different tolerability, particularly with regard to cardiovascular effects, and whether redosing after a 7-day washout results in cardiovascular effects (ie, loss of potential attenuation of cardiovascular effects with dose titration and multiple dosing). GLP-compliant and non-GLP-compliant cardiovascular safety studies in telemetered dogs with TAK-510 have demonstrated: (1) a dose-response of cardiovascular effects, where the lowest dose tested [REDACTED] results in an ~ED₅₀ (median effective dose) of maximal heart rate and blood pressure effects observed in dogs; (2) repeat-dosing at therapeutic doses results in a significant attenuation of cardiovascular effects following administration of the second daily dose. These data demonstrate that sub-therapeutic

doses can elicit minimal cardiovascular effects and that repeat dosing may elicit tachyphylaxis. Thus, Part 3 of this study is designed to test these concepts clinically to identify the appropriate tolerizing doses, escalation, and length of time of exposure that can potentially minimize cardiovascular effects at therapeutic doses.

6.3.3 Rationale for Endpoints

The PK and safety endpoints are standard for this type of study and are used widely and are recognized as reliable, accurate, and relevant. Additional PK parameters may be calculated if deemed necessary for the interpretation of the data.

6.3.4 Critical Procedures Based on Study Objectives: Timing of Procedures

For this study, the following procedures are critical:

Parts 1, 2, and 3:

- Timing of PK, BP, and telemetry assessments.
- All other procedures should be performed as close as possible (either before or after) the scheduled times.
- The order of priority can be changed during the study with joint agreement of the investigator and the sponsor.

Any nonscheduled procedures required for urgent evaluation of safety concerns take precedence over all routine scheduled procedures.

6.4 Procedure Modifications Permitted Within Protocol Parameters

This is a phase 1 study of TAK-510 in humans, and the PK and safety profiles of the compound are still being elucidated. This protocol is written to accommodate the dependence on evolving data and the inherent dynamic nature of phase 1 clinical studies. Minor changes in procedures, for example, changes to the specific dose regimen in any cohort or the specific timing of assessments, will be documented and may not require a protocol amendment or informed consent form update if the changes do not impact the burden of subjects or safety monitoring.

6.5 Study Beginning and End/Completion

6.5.1 Definition of Beginning of the Study

The overall study begins when the first subject signs the study informed consent form.

6.5.2 Definition of End of the Study

The overall study ends when the last subject completes the last planned or follow-up visit/interaction associated with a planned visit (this can be a phone contact), discontinues from the study, or is lost to follow-up (ie, the investigator is unable to contact the subject).

6.5.3 Definition of Study Discontinuation

Study discontinuation because of nonsafety reasons, such as the following:

- A finding (eg, PK, efficacy) from another nonclinical or clinical study using the study treatment results in the study being stopped for a nonsafety-related reason.
- Data from comparator(s), drug(s) of the same class, or methodology(ies) used in this study become available and results in the study being stopped for a nonsafety-related reason.
- The study is stopped because of nonscientific and nonsafety reasons, such as slow enrollment.

Study discontinuation because of safety reasons:

- Early study termination because of concerns of safety to the study subjects arising from clinical or nonclinical studies with the study treatment(s), comparator(s), drug(s) of the same class, or methodology(ies) used in this study.

6.5.4 Criteria for Premature Termination or Suspension of the Study

6.5.4.1 Criteria for Premature Termination or Suspension of Study

See Section [6.2](#) for study-specific stopping rules and additional criteria for premature termination or suspension of the study.

6.5.4.2 Procedures for Premature Termination or Suspension of the Study

In the event that the sponsor, an Institutional Review Board (IRB) and/or Independent Ethics Committee (IEC), or regulatory authority elects to terminate or suspend the study or the participation of an investigational site, a study-specific procedure for early termination or suspension will be provided by the sponsor; the procedure will be followed by applicable investigational sites during the course of termination or study suspension.

6.5.5 Criteria for Premature Termination or Suspension of a Site

6.5.5.1 Criteria for Premature Termination or Suspension of a Site

A study site may be terminated prematurely or suspended if the site (including the investigator) is found in significant violation of Good Clinical Practices (GCP), protocol, or contractual agreement, is unable to ensure adequate performance of the study, or as otherwise permitted by the contractual agreement.

6.5.5.2 Procedures for Premature Termination or Suspension of a Site

In the event that the sponsor, an IRB and/or IEC, or regulatory authority elects to terminate or suspend the study or the participation of an investigational site, a study-specific procedure for early termination or suspension will be provided by the sponsor; the procedure will be followed by applicable investigational sites during the course of termination or study suspension.

7.0 SELECTION AND DISCONTINUATION/WITHDRAWAL OF SUBJECTS

7.1 Inclusion Criteria

To be eligible for participation in this study, the subject must:

1. Understand the study procedures and agree to participate by providing written informed consent.
2. Be willing and able to comply with all study procedures and restrictions.
3. Be a healthy man or woman of nonchildbearing potential aged 18 to 55 years, inclusive, at the screening visit.
4. Continuous nonsmoker who has not used nicotine- and tobacco-containing products for at least 3 months prior to dosing and throughout the study.
5. Have a body mass index (BMI) ≥ 18 and ≤ 30.0 (kg/m^2) at the screening visit.
6. Be judged to be in good health (eg, no evidence of psychiatric, hepatic, renal, pulmonary, or cardiovascular disease) by the investigator, based on clinical evaluations including laboratory safety tests, medical history, physical examination, ECG, and vital sign measurements performed at the screening visit and before administration of the initial dose of study drug or invasive procedure.
7. Meet the following birth control requirements (see [Appendix D](#)):
 - Is a male subject who is sterile or agrees to use an appropriate method of contraception, including a condom with spermicidal cream or jelly, from the first dose of study drug until 5 half-lives after the last dose of study drug. No restrictions are required for a vasectomized male subject provided the subject is at least 1 year after bilateral vasectomy procedure before the first dose of study drug. A male subject whose vasectomy procedure was performed less than 1 year before the first dose of study drug must follow the same restrictions as a nonvasectomized man. Appropriate documentation of surgical procedure should be provided. Male subjects should agree to use condom with spermicide from screening time point if they cannot bring documentation for bilateral vasectomy.
 - Is a male subject who agrees not to donate sperm from the first dose of study drug until 5 half-lives after the last dose of study drug.
 - Is a female subject of nonchildbearing potential, defined by at least 1 of the following criteria:
 - a) Postmenopausal (defined as 12 months of spontaneous amenorrhea in females aged >45 years or 6 months of spontaneous amenorrhea in females aged >45 years with serum follicle-stimulating hormone (FSH) levels >40 mIU/mL). Appropriate documentation of FSH levels is required.
 - b) Surgically sterile by hysterectomy, bilateral salpingectomy, and/or bilateral oophorectomy with appropriate documentation of surgical procedure.

- c) Had a bilateral tubal ligation with appropriate documentation of surgical procedure.
- d) Has a congenital condition resulting in no uterus.

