4.3 Benefit/Risk Profile

This study represents the first study in humans with TAK-510.

The main objective of this study is to assess the safety and tolerability of TAK-510 in healthy subjects; as such, no clinical benefit is expected for study participants.

The potential risks of TAK-510 include HR increase, decreased BP, body weight loss, renal effects (proximal tubule vacuolation), elevated liver enzymes, injection site reaction, hypersensitivity, immunogenicity, postural hypotension, and myalgia. These potential risks are based on safety observations from the Good Laboratory Practice (GLP)-compliant nonclinical safety pharmacology and repeat-dose toxicity studies conducted with TAK-510, and clinical experience with TAK-510 [REDACTED] (refer to the TAK-510 Investigator's Brochure for additional details).

In nonclinical safety studies, the magnitude and duration of HR and BP changes in dogs were equivalent [REDACTED] at predicted therapeutic doses (sponsor data on file). Safety results from the [REDACTED] FIH study demonstrated a transient increase in HR within the first hour of [REDACTED] dosing as well as decreases in systolic BP and diastolic BP that were more prominent with postural changes (orthostatic) in some individuals within the first 2 hours postdosing ([REDACTED]; refer to the TAK-510 Investigator's Brochure for additional details). Postural hypotension is an identified risk [REDACTED]

[REDACTED] Given the findings of decreased BP and increased HR [REDACTED], it is hypothesized that TAK-510 causes vasodilation which leads to decreased BP and increased HR.

Audited draft results from a definitive rat embryo-fetal development study indicate fetal malformations were observed in a single fetus at each of the mid and high dose [REDACTED] [REDACTED]; the no-observed-adverse-effect level (NOAEL) for embryo-fetal development [REDACTED] (refer to investigator's brochure, Section 4.3.6 for additional details).

[REDACTED] All of these factors could contribute to the risk of immunogenicity and thus an assessment of antidrug antibodies (ADA) in all parts of the study will be included as part of the risk mitigation strategy.

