Subjects with a history of serious hypersensitivity to any medication or any component of TAK-510 formulation or with a history of significant multiple and/or severe allergies are excluded from this study. Subjects will be evaluated for the development of ADA as part of the study. The potential risks related to HR increase, decreased BP, body weight loss, renal effects (proximal tubule vacuolation), elevated liver enzymes, and injection site reactions will be monitored clinically and/or with laboratory tests and have been considered when determining the stopping rules for this clinical study.

In addition to the potential risks associated with study drug administration, there is minimal risk associated with study procedures, including scheduled periodic phlebotomy (limited to <575 mL). Total blood sampling volumes will not exceed approximately 319 mL (over 7 days of confinement) in Part 1, approximately 505 mL (over 11 days of confinement) in Part 2, and approximately 573 mL (over 10 days of confinement followed by 3 days of confinement after washout) in Part 3. The maximum volume of blood sampling on any single day is approximately 117 mL in Part 1, approximately 147 mL in Part 2, and approximately 82 mL in Part 3.

To minimize the risks to the subjects in this study, the sponsor considers the following measures to be appropriate: selecting TAK-510 doses with appropriate safety margins based on nonclinical study data; managing study eligibility criteria; excluding women of childbearing potential; prespecifying safety monitoring procedures, such as frequent BP assessments that include orthostatic BP measurements, telemetry, and 12-lead electrocardiogram (ECG); developing guidance for investigators; and using a clinical study facility where close monitoring can be performed and urgent medical care can be initiated rapidly as appropriate. Overall, the proposed risk mitigation plan is adequate to monitor subjects enrolled in the study.

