9.1.2 Inclusion and Exclusion

Each subject will be assessed through randomization, according to the eligibility criteria provided in Section [7.0](#).

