9.4 Childbearing Status and Methods of Contraception

9.4.1 Women of Childbearing Potential

Women of childbearing potential will be excluded from this study.

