9.4.1.1 Definition of Women of Childbearing Potential

A woman is considered of childbearing potential (ie, fertile) following menarche and until becoming postmenopausal, unless permanently sterile.

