9.4.2 Women of Nonchildbearing Potential

A female subject of nonchildbearing potential is defined as satisfying at least 1 of the following criteria:

- Postmenopausal: At least 12 months of spontaneous amenorrhea and an FSH concentration >40 mIU/mL.
- Surgically sterile by hysterectomy, bilateral salpingectomy, and/or bilateral oophorectomy with appropriate documentation of surgical procedure.
- Has no uterus as a result of a congenital condition.
- Has had a bilateral tubal ligation with appropriate documentation of surgical procedure.

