9.4.2.1 Contraception for Women of Nonchildbearing Potential

No contraception is required for women of nonchildbearing potential.

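### Inclusion criterion 7a admits women over 45 with only 6 months' amenorrhea and FSH above 40 mIU/mL, whom Section 9.4 classes as of childbearing potential and excludes

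*Protocol*

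**What the plan says.** Section 7.1, criterion 7, lists four ways for a woman to qualify as of nonchildbearing potential, and meeting one is enough. Route (a), postmenopausal status, has two branches. The first is 12 months' spontaneous amenorrhea at age over 45, with no FSH threshold attached. The second is "6 months of spontaneous amenorrhea in females aged >45 years with serum follicle-stimulating hormone (FSH) levels >40 mIU/mL".

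Section 9.4.2 defines the same status differently: "Postmenopausal: At least 12 months of spontaneous amenorrhea and an FSH concentration >40 mIU/mL". It sets no age condition and has no 6-month branch.

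Three neighbouring statements settle what follows for a woman who does not meet 9.4.2:

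- Section 9.4.1.1: "A woman is considered of childbearing potential (ie, fertile) following menarche and until becoming postmenopausal, unless permanently sterile".
- Section 9.4.1: "Women of childbearing potential will be excluded from this study".
- Section 9.4.2.1: "No contraception is required for women of nonchildbearing potential".

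On which section governs enrolment, Section 9.1.2 says "Each subject will be assessed through randomization, according to the eligibility criteria provided in Section" 7.0.

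**The concern.** The protocol gives two definitions of postmenopausal status, and they return opposite eligibility decisions for the same woman. The section that sites are told to use holds the shorter amenorrhea requirement.

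This bears on subject safety. Section 4.3 lists the exclusion among its measures to minimise risk: "managing study eligibility criteria; excluding women of childbearing potential; prespecifying safety monitoring procedures". The same section gives a reproductive-toxicity signal: "Audited draft results from a definitive rat embryo-fetal development study indicate fetal malformations were observed in a single fetus". One such fetus was found in the mid-dose group and one in the high-dose group. A woman enrolled through the 6-month branch would be dosed with no contraception required, although Section 9.4 says she should not be in the study. Part 1 gives a single dose, Part 2 gives 5 daily doses, and Part 3 gives 7 daily doses plus a redose.

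**Working it through.** No sample size, power or error rate is involved, so the check compares the texts and traces one woman through both sections.

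**Test case.** A woman aged 46 to 55 (the upper limit is set by inclusion criterion 3), with 6 to 11 months' spontaneous amenorrhea and FSH above 40 mIU/mL. She has had no hysterectomy, salpingectomy, oophorectomy or tubal ligation, and has a uterus.

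1. Section 7.1, route (a), second branch: she meets the age, amenorrhea and FSH conditions. One route suffices, so she is eligible on this criterion.
2. Section 9.4.2: she fails the 12-month requirement and has none of the other routes. She is not of nonchildbearing potential.
3. Section 9.4.1.1: not postmenopausal and not permanently sterile, so of childbearing potential.
4. Section 9.4.1: excluded.

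Steps 1 and 4 contradict each other.

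**All combinations.** Crossing age (45 or under, over 45), amenorrhea (6 to 11 months, 12 or more) and FSH (40 or under, above 40) gives 2 × 2 × 2 = 8 profiles. This tallies the logic only; it does not count women. The four not shown are admitted by neither section.

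| Profile | 7.1 route (a) | 9.4.2 |
|---|---|---|
| Over 45, 6–11 months, FSH >40 | admitted | not admitted |
| Over 45, ≥12 months, FSH >40 | admitted | admitted |
| Over 45, ≥12 months, FSH ≤40 | admitted | not admitted |
| 45 or under, ≥12 months, FSH >40 | not admitted | admitted |

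Section 7.1 admits 3 of 8 and Section 9.4.2 admits 2 of 8; they agree to admit only 1. The first row is the point raised here. The third and fourth rows are further mismatches, over the FSH threshold and the age condition, and they matter when choosing the repair.

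**Effect of the repair.** A single rule of age over 45 and at least 12 months' amenorrhea admits 1 of 8 profiles if FSH above 40 is required, or 2 of 8 if FSH is only documented. Both forms remove the first row and admit 0 profiles that 7.1 does not already admit. Copying 9.4.2 unchanged into 7.1 would newly admit 1 profile, the fourth row.

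**Supporting text.** Appendix D, cited by criterion 7, defines the postmenopausal state as 12 months without menses and says one FSH value is not enough without them. Its definition is attached to the female partners of male subjects, so it supports the point but does not carry it. The conflict between 7.1 and 9.4 stands without it.

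**The case against.** The wording conflict is not in dispute. The case against concerns its weight and the repair.

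- **Safeguards.** Exclusion criterion 5 bars anyone with a positive pregnancy test. Serum tests are scheduled at screening and on Day -2 in all parts, around discharge in Part 2, and on Days 8 and 13 in Part 3. As far as the broken tables can be read, they are also scheduled at early termination. Subjects are admitted on Day -2 and stay confined through the Part 1 dose, all five Part 2 doses and the first seven Part 3 doses. In Part 3 they are normally discharged on Day 8 and retested on Day 13, before the Day 14 redose. Appendix D adds pregnancy-avoidance guidance and withdrawal on pregnancy. What remains is a conception too early for the Day -2 or Day 13 test to detect, or one after discharge while drug persists. This stands and makes the risk small, but testing detects a pregnancy, whereas the exclusion is meant to prevent exposure.
- **Which rule operates.** Criterion 3 separately requires nonchildbearing potential, and criterion 7 points to Appendix D with its 12-month rule, so a careful site might apply 12 months. This is fair: that sites will use the 6-month branch is an inference from Section 9.1.2, and nothing shows that such a woman was enrolled. A site that has to find the stricter rule elsewhere is still working from a contradictory protocol.
- **Drafting error.** Both branches of route (a) carry the same over-45 condition, so one age may be a slip. That is plausible, but it does not reconcile the 6-month branch with Section 9.4.2. If the branch is intended, Section 9.4.2 is wrong and needs changing instead.
- **Reach of the repair.** Deleting the 6-month branch alone would answer the point. Requiring FSH above 40 also removes women over 45 with 12 months' amenorrhea and lower FSH. That is correct, and the FSH threshold is therefore a choice for the sponsor.

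**Conclusion.** The concern holds. Sections 7.1 and 9.4 give opposite eligibility decisions for women aged 46 to 55 with 6 to 11 months' amenorrhea, FSH above 40 mIU/mL and no other route to nonchildbearing status.

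The contradiction is certain on the text; its practical consequence is much less so. The number of women affected is not given and is assumed to be small. The hazard cannot be sized, because the rat findings are audited draft results, the embryo-fetal no-effect level is redacted, and the protocol as shown gives no half-life. No endpoint, analysis set or statistical result is touched. It should be corrected because it leaves a stated safety exclusion open to being bypassed.

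**What to change.** Delete the 6-month branch from Section 7.1 and keep the over-45 condition. State one postmenopausal rule in identical words in Sections 7.1 and 9.4.2: age over 45, at least 12 months' spontaneous amenorrhea, and a single explicit FSH requirement. FSH above 40 mIU/mL is the conservative choice, since Section 9.4.2 already requires it and FSH is already measured at screening. Do not copy Section 9.4.2 into 7.1 as it stands, because that would open the study to women aged 45 or under. Check whether any woman has already been enrolled through the 6-month branch.

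The cost is a wording amendment and slightly fewer eligible women aged 46 to 55. If FSH above 40 is required, women over 45 with at least 12 months' amenorrhea but FSH of 40 or less also lose eligibility under 7.1. No new procedure is needed.
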